## 11.2 Database management and quality control

Novartis personnel (or designated CRO) will review the data entered by investigational staff for completeness and accuracy. Electronic data queries stating the nature of the problem and requesting clarification will be created for discrepancies and missing values and sent to the investigational site via the EDC system. Designated investigator site staff are required to respond promptly to queries and to make any necessary changes to the data.

Concomitant treatments and prior medications entered into the database will be coded using the World Health Organization (WHO) Drug Reference List, which employs the Anatomical Therapeutic Chemical classification system. Medical history/current medical conditions and adverse events will be coded using the Medical Dictionary for Regulatory Activities (MedDRA) terminology.

Dates of screenings, randomizations, screen failures and study completion, as well as randomization codes and data about all study treatment (s) dispensed to the participant and all dosage changes will be tracked using an Interactive Response Technology (IRT). The system will be supplied by a vendor, who will also manage the database. The data will be sent electronically to Novartis (or a designated CRO) at specific timelines.

Each occurrence of a code break via IRT will be reported to the clinical team and monitor. The code break functionality will remain available until study shut down or upon request of Novartis.

Once all the necessary actions have been completed and the database has been declared to be complete and accurate, it will be locked and the treatment codes will be unblinded and made available for data analysis/moved to restricted area to be accessed by independent programmer and statistician. Any changes to the database after that time can only be made after written agreement by Novartis development management.

## 11.3 Site monitoring

Before study initiation, at a site initiation visit or at an investigator's meeting, a Novartis/delegated CRO representative will review the protocol and data capture requirements (i.e. eSource DDE or eCRFs) with the investigators and their staff. During the study, Novartis employs several methods of ensuring protocol and GCP compliance and the quality/integrity of the sites' data. The field monitor will visit the site to check the completeness of participant

records, the accuracy of data capture / data entry, the adherence to the protocol and to Good Clinical Practice, the progress of enrollment, and to ensure that study treatment is being stored, dispensed, and accounted for according to specifications. Key study personnel must be available to assist the field monitor during these visits. Continuous remote monitoring of each site's data may be performed by a centralized Novartis/ delegated CRO/ CRA organization. Additionally,

a central analytics organization may analyze data & identify risks & trends for site operational

parameters, and provide reports to Novartis clinical teams to assist with trial oversight.

The investigator must maintain source documents for each participant in the study, consisting of case and visit notes (hospital or clinic medical records) containing demographic and medical information, laboratory data, electrocardiograms, and the results of any other tests or assessments. All information on eCRFs must be traceable to these source documents in the participant's file. The investigator must also keep the original informed consent form signed by the participant (a signed copy is given to the participant).

The investigator must give the monitor access to all relevant source documents to confirm their consistency with the data capture and/or data entry. Novartis monitoring standards require full verification for the presence of informed consent, adherence to the inclusion/exclusion criteria, documentation of SAEs, and of data that will be used for all primary variables. Additional checks of the consistency of the source data with the eCRFs are performed according to the study-specific monitoring plan. No information in source documents about the identity of the participants will be disclosed.

# 12 Data analysis and statistical methods

Any data analysis carried out independently by the investigator should be submitted to Novartis before publication or presentation.

# 12.1 Analysis sets

For all analysis sets, participants will be analyzed according to the study treatment(s) received.

The safety analysis set will include all participants who received any study drug.

The PK analysis set will include all participants with at least one available valid (i.e. not flagged for exclusion) PK concentration measurement, who received any study drug and with no protocol deviations that impact PK data.

The PD analysis set will include all participants with available PD data and no protocol deviations with relevant impact on PD data.

# 12.2 Participant demographics and other baseline characteristics

Demographic and other baseline data including disease characteristics will be summarized descriptively by treatment group and overall utilizing the safety set.

Categorical data will be presented as frequencies and percentages. For continuous data, mean, standard deviation, median, minimum, and maximum will be presented. For selected parameters, 25th and 75th percentiles will also be presented.

Relevant medical histories and current medical conditions at baseline will be listed by treatment group.

#### 12.3 **Treatments**

The Safety set will be used for the analyses below. Categorical data will be summarized as frequencies and percentages. For continuous data, mean, standard deviation, median, 25th and 75th percentiles, minimum, and maximum will be presented.

The duration of exposure (in weeks) by treatment group and overall will be summarized using the safety set.

Concomitant medications and significant non-drug therapies prior to and after the start of the study treatment will be listed according to the Anatomical Therapeutic Chemical (ATC) classification system, by treatment group.

## 12.4 **Analysis supporting primary objectives**

## 12.4.1 **Definition of primary endpoint(s)**

The primary endpoint of the study is PVR, defined as the resistance against blood flow from the pulmonary artery to the left atrium measured in dyn·s·cm-5.

## 12.4.2 Statistical model, hypothesis, and method of analysis

# Primary endpoint – Pulmonary Vascular Resistance (PVR)

The change from baseline in PVR at Week 25 will be analyzed using a Bayesian approach (Fisch et al 2015) with Analysis of Covariance. The model includes treatment and WHO functional class as fixed effects and baseline value as a covariate. Contrast for treatment difference will be provided together with 80% two-sided credible intervals under Bayesian framework and the posterior probability that the treatment effect better than placebo will be derived.

To derive the prior distribution for the change from baseline in the placebo group, a meta-analysis (Neuenschwander et al 2010) on the change from baseline in PVR at Week 17/24 for the placebo groups (64 participants) from two historical clinical trials was conducted (Table 12-1). From this meta-analysis, the prior distribution for the change from baseline in PVR in the placebo group is a normal distribution with mean 38.5 dvn·s·cm^-5 and standard deviation 86.7 dyn·s·cm^-5, which corresponds to approximately 8 participants for the placebo group. This prior was used as a weakly informative prior for the placebo group at Week 25.

**Table 12-1** Historical data used for the meta-analysis to determine the informative prior on PVR for the placebo group

Trial	N	Treatment	Change from baseline (SE)
Selexipag PII	42 (3:1)	Selexipag (n=32)	-129.8 (54.8)
Sotatercept PII (PULSAR)	106 (~2:1)	Placebo (n=32)*	-16 (35.3)

\* Placebo arm represents patients on Standard of Care which may include Selexipag.

#### 12.4.3 Handling of intercurrent events of primary estimand

Not applicable.

#### 12.4.4 Handling of missing values not related to intercurrent event

Missing data will not be imputed.

## 12.4.5 Sensitivity analyses

The primary analysis will be repeated assuming a non-informative prior for placebo treatment group. This would allow us to capture the results without using any historical control data.

In the event of protocol deviations relevant for inclusion criteria or documented as any deviations from the standardized procedures for PVR collection, the primary analysis will be repeated excluding these subjects.

The underlying normality assumption for analysis of covariance (ANCOVA) will be evaluated. If normality assumption is not met, then alternative methods will be considered such as Hodges-Lehmann, or log-transformed data.

#### 12.4.6 Supplementary analysis

Not applicable.

## **Analysis supporting secondary objectives** 12.5

## 12.5.1 Efficacy and/or Pharmacodynamic endpoint(s)

Change from baseline for 6MWT will be analyzed based on mixed model repeated measures, adjusting for effects of treatment, visit as categorical factors and treatment\*visit and baseline\*visit interactions. Model based estimates of the mean effect will be reported for each treatment group along with the treatment difference, the 2-sided 80% confidence interval for treatment difference, and one-sided p-value.

Other efficacy endpoints including RHC, echocardiography parameters, PROs (emPHasis-10 and PAH-SYMPACT scores) and NT-proBNP will be summarized as change from baseline by visit and treatment group. Time to clinical worsening will be analyzed using survival models (i.e., Kaplan-Meier, cox regression) if adequate number of events occur during the study to characterize the survival curve. The hazard ratio and the corresponding 80% confidence intervals will be computed using the appropriate method.

If normality assumption is violated for any of the continuous outcomes, then appropriate transformation (i.e., log-transformed) of the data will be considered.

### 12.5.2 Safety endpoints

For all safety analyses, the safety set will be used. All listings will be presented by treatment group and tables will be presented by treatment group and overall.

Safety summaries (tables, figures) include only data from the on-treatment period with the exception of baseline data which will also be summarized where appropriate (e.g. change from baseline summaries). In addition, a separate summary for death including on treatment and post treatment deaths will be provided. In particular, summary tables for adverse events (AEs) will summarize only on-treatment events, with a start date during the on-treatment period (treatment-emergent AEs).

The on-treatment period lasts from the date of first administration of study treatment to the EOS visit (about 30 days after the date of the last actual administration of any study treatment).

## **Adverse events**

All adverse events summarized will be displayed by treatment group and overall. All adverse events listing will be presented by treatment group and participant.

The number (and percentage) of participants with treatment emergent adverse events (events started after the first dose of study medication or events present prior to start of double-blind treatment but increased in severity based on preferred term) will be summarized in the following ways:

- by treatment, primary system organ class and preferred term.
- by treatment, primary system organ class, preferred term and maximum severity.
- by treatment, Standardized MedDRA Query (SMQ) and preferred term.

Separate summaries will be provided for study medication related adverse events, death, serious adverse events, other significant adverse events leading to discontinuation. In case of sparse events in any of these categories occur, only a listing will be provided if deemed adequate.

A participant with multiple adverse events within a primary system organ class is only counted once towards the total of the primary system organ class.

All vital signs data will be listed by treatment group, participant, and visit/time and if ranges are available, abnormalities (and relevant orthostatic changes) will be flagged. Summary statistics and graphical presentations (e.g. boxplots) will be provided by treatment and visit/time.

## 12-lead ECG

PR, QRS, QT, QTcF, and RR intervals will be obtained from 12-lead ECGs for each participant during the study. ECG data will be read and interpreted (locally).

Categorical Analysis of QT/QTc interval data based on the number of participants meeting or exceeding predefined limits in terms of absolute QT/QTc intervals or changes from baseline will be presented. In addition, a listing of these participants will be produced (by treatment group).

All ECG data will be listed by treatment group, participant and visit/time, abnormalities will be flagged. Summary statistics and graphical presentations (e.g. boxplots) will be provided by treatment and visit/time.

## **Clinical laboratory evaluations**

All laboratory data will be listed by treatment group, participant, and visit/time and if normal ranges are available abnormalities will be flagged. Summary statistics will be provided by by visit/time for treatment group, and overall. Shift tables using the low/normal/high/ (low and high) classification will be used to compare baseline to the worst on-treatment value.

## 12.5.3 Pharmacokinetics

Descriptive summary statistics of LTP001 plasma concentration data will be provided by treatment, and visit/sampling time point, including the frequency (n, %) of concentrations below the LLOQ and reported as zero.

Summary statistics will include mean (arithmetic and geometric), standard deviation (SD), coefficient of variation (CV) (arithmetic and geometric), median, minimum, and maximum.

[figure not shown]
Descriptive summary statistics for LTP001 PK will include mean (arithmetic and geometric), SD, and CV (arithmetic and geometric), median, minimum, and maximum. An exception to this is Tmax where median, minimum, and maximum will be presented.

Table 12-2 Non-compartmental pharmacokinetic parameters

Cmax	The maximum (peak) observed plasma, blood, serum, or other body fluid drug concentration after single dose administration (ng x mL-1)
Tmax	The time to reach maximum (peak) plasma, blood, serum, or other body fluid drug concentration after single dose administration (h)

Novartis Confidential Page **83** of **94**Amended Protocol Version 03 (Clean) Protocol No. CLTP001A12201

## Amended Frotocol Version 00 (Clean

# 12.7 Interim analyses

An unblinded interim analysis (IA) will be planned for this trial.

The IA will be performed primarily to assess futility (non-binding) on PVR endpoint when approximately 20 participants complete the treatment period (Week 25). In addition, this IA will be utilized to evaluate safety, and efficacy relevant to other endpoints.

# 12.8 Sample size calculation

# 12.8.1 Primary endpoint(s)

# **Pulmonary Vascular Resistance (PVR)**

Approximately 44 participants including dropouts are planned to be randomized in a 3:1 ratio to receive LTP001 vs. placebo on top of Standard of Care (SoC). Dropout rate is considered to be around 10%.

The sample size calculation was based on the primary endpoint of change from baseline in PVR at Week 25. The criteria for this calculation is based on dual criteria:

1. An average change from baseline for PVR over placebo is 100 dyn·s·cm^-5 and

With a non-informative prior for the LTP001 group, and the obtained weakly informative prior for the placebo group, a sample size of 40 (3:1 ratio of LTP001: placebo) provides approximately 86% chance (power) of meeting the success criterion. Refer to Section 12.4.2 for further details. With approximately 20 participants completing the study at interim, the probability of considering stopping early for futility (non-binding) is approximately 47% in case of a placebo-like drug and approximately 1% in case the true treatment difference for PVR is 200 dyn·s·cm^-5, which is the statistically significant difference between drug and placebo in this PAH population.

Assumptions related to PVR variability will be evaluated at the time of interim analyses to consider re-estimation of sample size as appropriate.

# 13 Ethical considerations and administrative procedures

# 13.1 Regulatory and ethical compliance

This clinical study was designed and shall be implemented, executed and reported in accordance with the ICH Harmonized Tripartite Guidelines for Good Clinical Practice, with applicable local regulations (including European Directive 2001/20/EC, US CFR 21), and with the ethical principles laid down in the Declaration of Helsinki.

# 13.2 Responsibilities of the investigator and IRB/IEC

Before initiating a trial, the investigator/institution must obtain approval/favorable opinion from the Institutional Review Board/Independent Ethics Committee (IRB/IEC) for the trial protocol, written informed consent form, consent form updates, participant recruitment procedures (e.g., advertisements) and any other written information to be provided to participants. Prior to study start, the investigator is required to sign a protocol signature page confirming his/her agreement to conduct the study in accordance with these documents and all of the instructions and procedures found in this protocol and to give access to all relevant data and records to Novartis monitors, auditors, Novartis Quality Assurance representatives, designated agents of Novartis, IRBs/IECs, and regulatory authorities as required. If an inspection of the clinical site is requested by a regulatory authority, the investigator must inform Novartis immediately that this request has been made.

# 13.3 Publication of study protocol and results

The protocol will be registered in a publicly accessible database such as clinicaltrials.gov and as required in EudraCT. In addition, after study completion (defined as last patient last visit) and finalization of the study report the results of this trial will be submitted for publication and posted in a publicly accessible database of clinical trial results, such as the Novartis clinical trial results website and all required Health Authority websites (e.g. Clinicaltrials.gov, EudraCT etc.).

For details on the Novartis publication policy including authorship criteria, please refer to the Novartis publication policy training materials that were provided to you at the trial investigator meetings.

## 13.4 **Quality Control and Quality Assurance**

Novartis maintains a robust Quality Management System (QMS) that includes all activities involved in quality assurance and quality control, to ensure compliance with written Standard Operating Procedures as well as applicable global/local GCP regulations and ICH Guidelines.

Audits of investigator sites, vendors, and Novartis systems are performed by auditors, independent from those involved in conducting, monitoring or performing quality control of the clinical trial. The clinical audit process uses a knowledge/risk based approach.

Audits are conducted to assess GCP compliance with global and local regulatory requirements, protocols and internal SOPs, and are performed according to written Novartis processes.

## 13.5 **Participant Engagement**

The following participant engagement initiatives are included in this study and will be provided, as available, for distribution to study participants at the time-points indicated. If compliance is impacted by cultural norms or local laws and regulations, sites may discuss modifications to these requirements with Novartis.

- Thank You letter
- Plain language trial summary after CSR publication

#### 14 Protocol adherence

This protocol defines the study objectives, the study procedures and the data to be collected on study participants. Additional assessments required to ensure safety of participants should be administered as deemed necessary on a case by case basis. Under no circumstances including incidental collection is an investigator allowed to collect additional data or conduct any additional procedures for any purpose involving any investigational drugs under the protocol, other than the purpose of the study. If despite this interdiction prohibition, data, information, observation would be incidentally collected, the investigator shall immediately disclose it to Novartis and not use it for any purpose other than the study, except for the appropriate monitoring on study participants.

Investigators ascertain they will apply due diligence to avoid protocol deviations. If an investigator feels a protocol deviation would improve the conduct of the study this must be considered a protocol amendment, and unless such an amendment is agreed upon by Novartis and approved by the IRB/IEC and Health Authorities, where required, it cannot be implemented.

#### 14.1 **Protocol amendments**

Any change or addition to the protocol can only be made in a written protocol amendment that must be approved by Novartis, health authorities where required, and the IRB/IEC prior to implementation.

Only amendments that are required for participant safety may be implemented immediately provided the health authorities are subsequently notified by protocol amendment and the reviewing IRB/IEC is notified.

Notwithstanding the need for approval of formal protocol amendments, the investigator is expected to take any immediate action required for the safety of any participant included in this study, even if this action represents a deviation from the protocol. In such cases, Novartis should be notified of this action and the IRB/IEC at the study site should be informed according to local regulations.

Protocol No. CLTP001A12201

## Appendix 1: Clinically notable laboratory values and vital signs 16.1

Systolic blood pressure > 165 mm Hg or < 80 mm Hg in absence of arterial hyper- or hypertension at baseline

Diastolic blood pressure > 109 mm Hg or < 50 mm Hg in absence of arterial hyper- or hypertension at baseline

Pulse rate > 99 bpm or < 50 bpm and change by 20 bpm or more from baseline

QTcF increase by > 60 ms

All QTcF > 500 ms

QTcF > 480 ms if normal at baseline

QRS-Duration > 120 ms when normal at baseline.

PR - value > 220 ms when normal at baseline

AV-block > Grade 2a

Values need to be noted and their clinical significance in light of the underlying PAH condition needs to be considered (does condition cause symptoms; is condition a sign for disease progression; is condition a potential side effect of LTP001 or other PAH directed therapy?)

# 16.2 Appendix 2: Liver event and laboratory trigger definitions & follow-up requirements

To ensure participant safety and enhance reliability in determining the hepatotoxic potential of an investigational drug, a standardized process for identification, monitoring and evaluation of liver events has to be followed.

Please refer to Table 16-1 in Appendix 5 for complete definitions of liver laboratory triggers.

Once a participant is exposed to study treatment, every liver event defined in Table 16-1 should be followed up by the Investigator or designated personnel at the trial site, as summarized below. Since deterioration of PAH may result in increases of liver values it should be checked if an increase of liver values might be secondary to a deterioration of right heart failure. Liver chemistry tests (i.e. ALT, AST, TBL, PT/INR, ALP and G-GT) to confirm elevation. Increased liver values considered secondary to deterioration of right heart function are not considered liver events.

- 1. Liver chemistry repeats will be performed using the central laboratory. If results will not be available from the central laboratory, then the repeats can also be performed at a local laboratory to monitor the safety of the participant. If a liver event is subsequently reported, any local liver chemistry tests previously conducted that are associated with this event should have results recorded on the appropriate CRF.
- 2. If the initial elevation is confirmed, close observation of the participant will be initiated, including consideration of treatment interruption if deemed appropriate.
- 3. Discontinuation of the investigational drug (refer to the Discontinuation of study treatment Section 9.1.1 Discontinuation from study treatment), if appropriate
- 4. Hospitalization of the participant if appropriate
- 5. Causality assessment of the liver event
- 6. Thorough follow-up of the liver event should include, as per the investigator's discretion to allow for a causality assessment: serology tests, imaging and pathology assessments, hepatologist's consultancy; obtaining more detailed history of symptoms and prior or concurrent diseases, history of concomitant drug use, exclusion of underlying liver disease.

All follow-up information and procedures performed must be recorded as appropriate in the eCRF.

Table 16-1 Liver event and laboratory trigger definitions

	Definition/ threshold	
Liver laboratory triggers	ALT or AST > 5 × ULN	
If ALT, AST and total bilirubin normal at baseline:	
 
ALP > 2 × ULN (in the absence of known bone pathology)
 
	
	
 
Total bilirubin > 3 × ULN (in the absence of known Gilbert syndrome)
 
	
	
 
ALT or AST > 3 × ULN and INR > 1.5
 
	

	
 
Potential Hy's Law cases (defined as ALT or AST > 3 × ULN and Total bilirubin > 2 × ULN [mainly conjugated fraction] without notable increase in ALP to > 2 × ULN)
 

	
 
Any clinical event of jaundice (or equivalent term)
 

	
 
ALT or AST > 3 × ULN accompanied by (general) malaise, fatigue, abdominal pain, nausea, or vomiting, or rash with eosinophilia
 

	
 
Any adverse event potentially indicative of a liver toxicity
 

If ALT or AST abnormal at baseline:	
 
ALT or AST > 3x baseline or > 300 U/L (whichever occurs first)
 

Notify Novartis study lead and medical lead of any finding of a liver event identified not explained by PAH worsening for further follow-up assessments.

Table 16-2 Follow up requirements for liver laboratory triggers - ALT, AST, TBL

	ALT	TBL	Liver Symptoms	Action
ALT increase without bilirubin increase:				
	If normal at baseline: ALT > 3 x ULN	Normal For participants with Gilbert's syndrome: No change in baseline TBL	None	No change to study treatment
	If elevated at baseline:  ALT > 2 x baseline or > 300 U/L (whichever occurs first)			
 
Measure         ALT, AST,         ALP, GGT,         TBIL, INR,         albumin, CK,         and GLDH in         48-72 hours.
 
Follow-up for         symptoms.
 

	If normal at baseline:  ALT > 5 x ULN for more than two weeks  If elevated at baseline:  ALT > 3 x	Normal For participants with Gilbert's syndrome: No change in baseline TBL	None	
 
Interrupt study treatment
 
Measure ALT, AST, ALP, GGT, TBIL, INR, albumin, CK,
 

	baseline or > 300 U/L (whichever occurs first) for			and GLDH in 48-72 hours.

Amended Protocol Version 03 (Clean)

	ALT	TBL	Liver Symptoms	Action
	more than two weeks			Follow-up for symptoms.
	If normal at baseline: ALT > 8 x ULN	Normal	None	
 
Initiate close monitoring and workup for competing
 

ALT increase with	bilirubin increase:			
	If normal at baseline: ALT > 3 x ULN	TBL > 2 x ULN (or INR > 1.5) For participants	None	

etiologies.

Study treatment can

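### Table 16-1 sets liver triggers on ALT or AST, but every Table 16-2 threshold is on ALT alone, so a case with only AST above threshold matches no Table 16-2 row

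*Protocol*

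**What the plan says.** Protocol 9.1.1 sends investigators to Appendix 2 (16.2) when a liver event raises the question of stopping study treatment. In Table 16-1, five triggers are worded for either enzyme:

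1. "ALT or AST > 5 × ULN", with a normal baseline.
2. Either enzyme above 3 × ULN with INR above 1.5.
3. The item that begins "Potential Hy's Law cases (defined as ALT or AST", which also needs total bilirubin above 2 × ULN without a notable ALP rise.
4. Either enzyme above 3 × "ULN accompanied by (general) malaise, fatigue, abdominal pain, nausea, or vomiting, or rash with eosinophilia".
5. Under "If ALT or AST abnormal at baseline", either enzyme above 3 × baseline or above 300 U/L.

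Table 16-2, "Follow up requirements for liver laboratory triggers - ALT, AST, TBL", gives the graded responses. Its threshold column is headed ALT. Its two blocks are "ALT increase without bilirubin increase" and the counterpart with a bilirubin increase. In the body of the table, AST appears only among the tests to be measured. The Action column includes "Interrupt study treatment", a retest at 48-72 hours, and a restart limit: another cause must be found and liver enzymes must be back at baseline.

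Other provisions also apply to a liver event:

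- The general steps in 16.2, largely repeated in 10.2.1, call for repeat liver tests that include AST, close observation, and interruption, discontinuation or hospitalization where judged appropriate. Section 16.2 adds causality assessment.
- The sponsor must be told of any liver event not explained by PAH worsening.
- Table 16-3 has a row for any adverse event suggesting liver toxicity. It asks the site to consider interruption or discontinuation.
- Section 9.1.1 requires discontinuation where continuing might put the participant at risk.

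**The concern.** Appendix 2 is meant to give sites a standardized process. Table 16-1 treats the two transaminases as interchangeable, and the Table 16-2 title suggests that both were meant to be covered, but no Table 16-2 criterion can be met by AST. The same clinical picture is therefore handled by a table row if ALT is the raised enzyme, and by judgement if only AST is.

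Potential Hy's law cases and cases with raised INR or symptoms are the ones where a fixed rule is most useful. About 44 × 3/4 = 33 participants are to receive a first-in-class drug for 24 weeks. Section 6.6 otherwise bars dose interruptions, which makes an explicit liver rule more useful to a site.

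**Working it through.** No power or error-rate figure is involved. The check sets the two tables side by side.

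**Thresholds in Table 16-2**

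| Row | Situation | Normal baseline | Elevated baseline | Count |
|---|---|---|---|---|
| 1 | Bilirubin normal, no symptoms | ALT > 3 × ULN | ALT > 2 × baseline or > 300 U/L | 2 |
| 2 | As row 1, for more than two weeks | ALT > 5 × ULN | ALT > 3 × baseline or > 300 U/L | 2 |
| 3 | Bilirubin normal, no symptoms | ALT > 8 × ULN | none | 1 |
| 4 | Bilirubin or INR raised | ALT > 3 × ULN | ALT > 2 × baseline or > 300 U/L | 2 |
| 5 | Listed symptoms | ALT > 3 × ULN | ALT > 2 × baseline or > 300 U/L | 2 |

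The total is 2 + 2 + 1 + 2 + 2 = 9 thresholds. All nine name ALT and none names AST.

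**Illustrative cases, one per trigger**

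| Trigger | Higher / lower enzyme | Row if AST is higher | Row if ALT is higher |
|---|---|---|---|
| 1 | 6 / 2 × ULN, bilirubin normal, no symptoms | none | 1 at first; 2 once past two weeks |
| 2 | 4 / 2 × ULN, INR 1.6 | none | 4 |
| 3 | 4 / 2 × ULN, bilirubin 2.5 × ULN (mainly conjugated), ALP normal | none | 4 |
| 4 | 4 / 2 × ULN, vomiting | none | 5 |
| 5 | 3.5 / 1.5 × baseline, elevated baseline, lower value not above 300 U/L | none | 1 at first |

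The last column holds for these cases only. An ALT of 4 × ULN with malaise, or with rash and eosinophilia, meets trigger 4. Read literally, it also matches no Table 16-2 row: row 1 requires no symptoms, and row 5 lists only severe fatigue, nausea, vomiting and right upper quadrant pain.

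**Edge of the gap.** It opens only when ALT is at or below 3 × ULN or, with an elevated baseline, at or below both 2 × baseline and 300 U/L. With AST 6 × ULN, ALT 3.5 × ULN and bilirubin 2.5 × ULN, row 4 applies and there is no gap.

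**What the ALT case receives.** In cases 1 and 5 the ALT version at first reaches only row 1, which leaves treatment unchanged and asks for a retest at 48-72 hours. Little is lost there unless the rise persists or climbs. In cases 2 to 4 the ALT version reaches row 4 (bilirubin column: "TBL > 2 x ULN (or INR > 1.5") or row 5.

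The action in rows 4 and 5 depends on the table layout. In the text read from the PDF, "Interrupt study treatment" stands beside row 2 only, which gives 1 of 5 rows with mandatory interruption. If the Action cell is merged across rows 2 to 5, the count is 4 of 5. Two features favor a merged cell: one action sentence begins beside row 3 and ends beside row 4, and the restart limit beside row 4 presupposes that treatment was stopped.

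**Nearest numeric row for case 3.** With ALT below threshold, the only numeric bilirubin row near 2.5 × ULN is the Table 16-3 band from above 1.5 to 3.0 × ULN. That row keeps treatment going and repeats liver tests within 48-72 hours.

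**The case against.** The strongest counter-argument is that nothing goes unmanaged. The general steps apply to every Table 16-1 event, and the Table 16-3 adverse-event row sets actions of its own. A clinically significant or symptomatic laboratory abnormality normally counts as an adverse event under 10.1.1. Table 16-2 was also never a one-to-one map: ALP above 2 × ULN and clinical jaundice have no dedicated row either. Since the title already names AST, a sensible investigator may apply the ALT rows to AST. There is also DMC review and at least monthly blinded safety review.

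Most of this stands. A reader might infer that a case with only AST above threshold has no follow-up, but the provisions above rule that out. A reader might also infer that every ALT case carries a fixed interruption rule. The documents do not establish that: two of the five illustrated ALT cases at first leave treatment unchanged, and interruption in rows 4 and 5 rests on a merged cell. Nor does Table 16-3 direct sites to keep dosing a potential Hy's law case, because the row in question is for isolated bilirubin rises and AST is raised here.

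The counter-argument does not remove the mismatch. The fallback routes leave interruption to judgement, and none sets a restart limit. Relying on investigators to read AST into ALT thresholds is not a standardized process.

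**Conclusion.** The inconsistency is real and narrow. All nine Table 16-2 thresholds name ALT, so a case with AST above and ALT below threshold matches no Table 16-2 row under any of the five either-enzyme triggers. It matters for three of them: above 3 × ULN with INR above 1.5, potential Hy's law, and above 3 × ULN with symptoms.

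The ALT-only wording is plain on any layout. The size of what is lost in the three serious cases is less certain, because mandatory interruption there depends on the Action cell being merged. The documents give no frequency for such cases, and rises secondary to right heart failure are excluded as liver events. This is a safety-rule correction that should be made. It does not touch the endpoint, sample size or analysis.

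**What to change.** In Table 16-2:

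- Change ALT to ALT or AST in the bilirubin/INR row and the symptom row, for normal and elevated baseline, and in the matching block heading and column header.
- Align the symptom list with the Table 16-1 symptom trigger, which also closes the malaise and rash gap for ALT.
- Extending the wording to the isolated-transaminase rows is optional. If they stay on ALT alone, say that isolated AST rises follow the general steps.

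The cost is a wording edit to one table at the next amendment and a notice to sites. AST is already in the routine chemistry panel (8.4.1), so no test is added. The downside is a few extra interruptions for AST rises of non-hepatic origin. The CK, GLDH and hemolysis tests already in the liver follow-up panel help to identify those.
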